2. STUDY PLAN AND PROCEDURES

2.1 Study design

The MAAAGI-trial is a population-based multi-center, prospective, parallel group, randomized, open label trial with blinded outcome assessment to assess if metformin up to 2g daily over a five-year period will reduce AAA growth in patients who do not have diabetes.

Patients will be recruited from a cohort of patients with diagnosed AAA at the following seven Swedish sites; 1) Uppsala University hospital, Uppsala, 2), Skåne University hospital, Malmö, 3) Gävle county hospital, Gävle, 4) Västerås county hospital, Västerås. 5) Karlstad county hospital, Karlstad 6) Falun county hospital, Falun, and 7) Umeå University Hospital, Umeå.

The patients should have a maximum aortic diameter of 30-49mm for men and 30-44mm for women, not have diabetes and be expected to tolerate metformin.

A total of 500 patients with AAA will be included in the study, 250 in each study arm. Patients will be randomised to metformin or standard care in a 1:1 ratio.

The patients are scheduled for one enrolment visit, eight study visits and ten phone contacts for those randomized to metformin (three to support titration of study drug) and seven phone contacts for those randomized to standard care. The study visits will take place at the vascular laboratory at the respective surgical departments for clinical examination and blood sampling and at the CT units at the radiology departments where CT-imaging will be performed.

After a run in phase to support titration of metformin, visits and phone contacts are scheduled to alternate every three months until 24 months and twice yearly thereafter. CT imaging and AAA US will be performed at baseline, 24 months and end of study, as well as if necessary according to clinical routine. Study drug will start at baseline and continue through completion.

End of study is defined as 1) study completion at 60 months, or 2) discontinuation from study before that for any reason, for example due to AAA repair or patients will.

When all patients have completed the 24-month follow-up (including imaging) an interim analysis will be performed to assess for efficacy and safety; if there is no trend towards a positive effect or signs of a harmful effect of metformin, the study will be stopped at this phase.

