4.2 Withdrawal from study

Patients may be discontinued from the study at any time, at the discretion of the investigator.

Patients are free to discontinue their participation in the study at any time for any reason.

Patients who discontinue from the study should always be asked about the reason(s) for the discontinuation (and informed about their right not to disclose their reason for doing so) and the presence of any adverse events (AEs). If possible, they should always be seen and assessed by an investigator and asked to perform completion outcome measures, including CT, US and QoL questionnaires. A pre-operative CT may be used for follow up should indication to operate the aorta arise. Adverse events should be followed up.

Study treatment should be stopped in the following cases: development of diabetes, persistent renal failure with GFR<45ml/min, severely deteriorating health, aortic surgery or onset of exclusion criteria.

If the study medication is stopped, patients will be asked to remain in the study and follow the other procedures according to the protocol. All randomised patients remain in the group they were originally allocated to for the purpose of intention-to-treat (ITT) analyses.

Patients who discontinue the study will not be replaced.

Sponsor has to be informed if a patient is withdrawn by any reason before study end. The "End of study" form must be filled out by the investigator and the reason should be stated.

The study number will not be reused if a patient is withdrawn.

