5.1.2 Imaging

At baseline, 24 months and completion, the aorta will be examined by non-contrast enhanced CT with 1 mm slices or thinner from the jugulum to the groins.

At enrolment, 24 months and completion the abdominal aorta will be examined by US. The assessment of abdominal aortic diameter with US will be done by the local US technician, using the standardized technique measuring the largest anterior-posterior diameter from leading edge to leading edge perpendicular to the blood flow in the aneurysm. Inclusion criteria will be based on US determined diameter.

If a subject withdraws from the study due to operative need of the aorta, the preoperative CT will be used for analysis in the study. The assessment of aortic diameter on CT will be done using outer edge to outer edge perpendicular to blood flow. Volumetric AAA analysis of CT images will be performed using manual drawing of the vessel wall contours in axial slices of the entire abdominal aortic as well as semiautomatic measures in 3mensio, Pie Medical, Maastricht. Analysis will start at the slice just below the most distal renal artery excluding accessory renal arteries and end at the slice just above the aortic bifurcation. Measures of perivascular adipose tissue will be made adjacent to the aorta.

All CT assessment (diameter and volume) will be done at a core lab at the Department of Radiology, Uppsala university hospital, Uppsala. The CT identification is the four digits enrolment code. The reviewer will be blinded regarding treatment allocation.

CT images will also be reviewed by local radiologists according to GCP at respective hospital. Accidental findings of unrelated pathology on the CT scan will be dealt with as appropriate by investigator at respective site.

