8.1 Analysis set

All patients for whom a signed informed consent was obtained and an eCRF was started will be accounted for.

The Safety Analysis Set will include all patients who received at least one dose of study drug.

An intention-to-treat (ITT) analysis will include all randomised patients who received at least one dose of study drug and for whom at least one post dose observation for an efficacy endpoint is recorded.

The per-protocol analysis (PPA) consists of patients who sufficiently complied with the protocol. Inclusion in the PPA will require at least the following:

- An at least 80% compliance with the intended use will be accepted as per protocol.
- No major protocol deviations.

• Measure of primary efficacy endpoint at 60 months after baseline, and at 24 months for the interim analysis.

All efficacy analyses will be performed as both ITT and PPA. The ITT analyses is to be considered as main and the PPA as supportive.

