8.3 Statistical analysis

The primary efficacy end-point is the between groups difference in mean annual AAA growth over 60 months. AAA growth will be analysed using an analysis of covariance (ANCOVA) model where AAA growth at 60 months is the dependent variable and treatment group and baseline AAA is included as independent variables. The results will be presented as the estimated group difference with 95 % confidence intervals at 60 months.

Similar methods will be used to assess growth as log transformed CT-volume and ultrasound diameter. Analysis of other outcomes: 1) Laboratory data and perivascular adipose tissue are exploratory endpoints and will be reported with descriptive statistics and evaluated with appropriate inferential statistics, 2) Patient reported outcome (QoL questionnaires) will be analysed using non-parametric test (Wilcoxson rank-sum test), 3) Pre-defined clinical events,

such as AAA-repair, rupture and death, are expected to be few, and the presentations will use descriptive statistics, 4) Economic analysis: Will be performed adopting a health system perspective. The cost-effectiveness analysis will produce an incremental cost effectiveness ratio as an estimated cost per surgical procedure avoided.

Handling of missing values: The primary analyses will be performed among patients with a measured value at the specific time point. However, as the number of missing values might be substantial several sensitivity analyses of the primary analysis will be performed:

- Multiple imputation (with different assumptions)
 - Assume that drop-outs respond according to randomized group
 - Assume that drop-outs respond according to control group
- Fixed imputation depending on reason for drop-out
 - For clinical events, such as AAA-repair, rupture and death, impute worst possible value
 - For other events impute using a maximum likelihood function

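### The drop-out sensitivity analyses run on an ITT set that omits patients with no post-dose efficacy observation, so some early leavers and early non-aneurysm deaths are never imputed

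*Combined protocol and SAP*

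**What the plan says.** Section 8.1 sets two conditions for the ITT set. The second, which matters here, limits it to patients "for whom at least one post dose observation for an efficacy endpoint is recorded". The same section states: "All efficacy analyses will be performed as both ITT and PPA", with ITT as the main analysis. The per-protocol set requires the primary measurement at month 60 (month 24 at the interim).

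Section 8.3 bases the primary analysis on patients measured at the time point. It then adds sensitivity analyses because much may be missing. One is multiple imputation under two assumptions, the second being "Assume that drop-outs respond according to control group". The other imputes by reason for drop-out and gives the worst value after aneurysm repair, rupture or death. No analysis set is named for either.

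On timing, section 5.1.2 says "At enrolment, 24 months and completion the abdominal aorta will be examined by US". Table 1 puts CT and quality of life at the same follow-up times. Section 2.1 counts early discontinuation as end of study. Section 4.2 asks leavers for CT, ultrasound and questionnaires where this can be done. It also says: "All randomised patients remain in the group they were originally allocated to for the purpose of intention-to-treat (ITT) analyses".

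**The concern.** For the primary endpoint, the observation condition matters only in the imputation analyses. The primary analysis already needs a measured month-60 value, so the condition removes nobody further from it. The per-protocol set has no missing month-60 values to impute. That leaves imputation on the ITT set, where the condition removes some of the patients whom imputation is meant to represent.

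Two planned analyses are affected. Control-based imputation is meant to show how far the effect shrinks if leavers do no better than controls; leaving out some metformin leavers understates that shrinkage. The worst-value rule names death as a trigger, yet a patient who dies of a non-aneurysm cause before any follow-up measurement is not in the set to receive the value.

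The trial is open label, and section 8.4 expects 30% drop-out over five years. Losses need not be alike in the two arms.

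**Working it through.** **Who falls outside the set**

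| Patient, before month 24 | Post-dose efficacy observation? | Open to imputation? |
|---|---|---|
| Stops drug, stays in the study (4.2) | Yes, at month 24 if followed | Yes |
| Leaves, gives exit CT, ultrasound or QoL (2.1, 4.2) | Yes | Yes |
| Leaves for aortic surgery (5.1.2, 8.2.2) | Pre-operative CT, and the event itself | Yes |
| Rupture (8.2.2) | The event can count | Arguably yes |
| Leaves, no exit measure, no aneurysm event | No | No |
| Dies of a non-aneurysm cause, nothing measured | No | No |

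The concern is the last two rows.

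**Inputs from section 8.4.** Growth is 3 mm/year with SD 2.17, the reduction is 30%, and drop-out is 30% over five years. The planned effect is 0.30 × 3 = 0.90 mm/year. As a check on these inputs, the plan's 184 patients reproduce: 2 × (1.960 + 0.842)² × 2.17² / 0.90² = 91.3, so 92 per arm and 184 in all.

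**Assumptions not in the documents.** The 30% loss applies to the metformin arm. Leavers keep no benefit. A share *e* of that arm leaves with no efficacy observation.

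**Control-based estimate**

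- All randomised patients: 0.90 × (1 − 0.30) = 0.63 mm/year.
- Planned set: 0.90 × 0.70 / (1 − *e*) = 0.63 / (1 − *e*).
- Ratio of the two: 1 / (1 − *e*).

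**Plausible values of *e***

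- Even drop-out: 30% × 24/60 = 12% gone by month 24.
- Constant hazard: 1 − 0.70^(24/60) = 13.3%.
- Halve these if half of the early leavers give an exit observation; *e* is zero if all do.

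| Scenario | *e* | Planned set, mm/year | Overstatement against 0.63 |
|---|---|---|---|
| All leavers give exit data | 0% | 0.63 | 0% |
| Even drop-out, half give exit data | 6% | 0.67 | 6% |
| Constant hazard, half give exit data | 6.6% | 0.67 | 7% |
| Even drop-out, none give exit data | 12% | 0.72 | 14% |
| Constant hazard, none give exit data | 13.3% | 0.73 | 15% |
| High early loss, none give exit data | 20% | 0.79 | 25% |

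The last row puts two-thirds of the five-year loss (20/30) before month 24, with nothing measured at exit. It is an upper illustration, not an expectation.

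The effect on the worst-value analysis cannot be sized, because the documents give no rate of early non-aneurysm death.

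**The case against.** The strongest reply is that the plan already collects exit data. End-of-study imaging covers early discontinuation, leavers are asked for all three outcome measures, and a pre-operative CT is used after withdrawal for surgery. Month 24 is therefore not the first possible observation. This stands, and it is why the range starts at zero. But exit measures depend on the patient agreeing, and someone who has died cannot give one.

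Section 8.3 also does not say that imputation is confined to the ITT set. That is an inference from the statement in 8.1 covering all efficacy analyses. The worst-value rule for death could be read as implying a wider set. If so, the two sections disagree and need reconciling. Likewise, the sentence in 4.2 may govern which arm a patient is counted in rather than who enters the set, so it is supporting evidence only.

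Biomarkers are listed as efficacy variables in 8.2.2, and Table 1 marks blood samples at month 12, with biobank samples at two sites. If those count, some early leavers there would enter the set. Section 5.1.1 places the scientific samples only at baseline, month 24 and completion, so this is unclear.

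Imputation by randomised group would hardly change, since patients with only baseline data add almost nothing to it.

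A reader might infer three stronger points that the documents do not support:

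- That early leavers and early deaths appear in no analysis. Section 8.1 says "The Safety Analysis Set will include all patients who received at least one dose of study drug", and 8.3 presents deaths descriptively.
- That gastrointestinal intolerance during titration is the main route out of the set. Section 4.1 provides for slower titration and dose reduction, and 4.2 asks patients who stop the drug to stay in follow-up.
- That the control-based analysis cannot show dilution. At *e* = 12% it still falls from 0.90 to 0.72 mm/year.

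Finally, the other ITT condition, "will include all randomised patients who received at least one dose of study drug", read literally excludes the standard-care arm. That is a separate defect. Defining ITT as all randomised patients would cure both, but repairing the dose wording alone would leave this one in place.

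**Conclusion.** The point holds in a limited form. Followed as written, the imputation analyses miss patients who leave before month 24 with no exit measure and no surgery or rupture, and patients who die early of a non-aneurysm cause. This conflicts with the plan's own worst-value rule for death and sits poorly with 4.2.

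The observed-case primary estimate does not change. What changes is the control-based estimate and the handling of early deaths. The control-based overstatement runs from 0% to about 15% under even or constant-hazard drop-out, and to 25% in the high early-loss case. These figures assume 30% loss in the metformin arm, no retained benefit in leavers, and imputation on the ITT set. Drop-out timing and exit-assessment rates are not in the documents, so no single value can be claimed. The planned robustness check is incomplete, and this should be corrected before the data are analysed.

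**What to change.** In sections 8.1 and 8.3, state that the multiple-imputation and reason-based sensitivity analyses include all randomised patients in both arms, using the baseline CT and without the post-dose-observation condition. State explicitly that the worst-value rule applies to deaths before any follow-up measurement. Report by arm the number of patients with no post-baseline efficacy observation.

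This is a change of wording and needs no new visits or data. Its cost is that the sensitivity estimates may be less favourable to metformin.

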8.2.2 Secondary variables

Secondary efficacy variables are; 1) difference in log-transformed AAA-volume determined by CT at 24 and 60 months vs at baseline (Log-transformation is undertaken because AAA volumes appear to follow a right-skewed distribution based on in house data), 2) difference in AAA-diameter determined by US at 24 and 60 months vs at baseline, 3) difference in circulating inflammation and matrix remodelling biomarkers assessed by established assays, 4) difference in quality of life score at 24 and 60 months vs at baseline, 5) difference in need for AAA surgery and aneurysm rupture at 24 and 60 months and 6) cost effectiveness of metformin treatment 2 g daily to reduce need for prophylactic surgery of AAA.

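### The per-protocol set requires a 60-month CT growth measure but is also used for AAA surgery, rupture, quality of life and cost, so its event comparison is depleted and selected on the outcome

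*Combined protocol and SAP*

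**What the plan says.** Section 8.1 lists three minimum conditions for the per-protocol set: at least 80% compliance, no major deviation, and "Measure of primary efficacy endpoint at 60 months after baseline, and at 24 months for the interim analysis". The same section gives the set's scope and rank: "All efficacy analyses will be performed as both ITT and PPA", and "The ITT analyses is to be considered as main and the PPA as supportive".

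The secondary efficacy variables in 8.2.2 include quality of life (item 4), "difference in need for AAA surgery and aneurysm rupture at 24 and 60 months" (item 5) and "cost effectiveness of metformin treatment 2 g daily to reduce need for prophylactic surgery of AAA" (item 6). Section 8.3 expresses the economic result as an "estimated cost per surgical procedure avoided" and presents clinical events with descriptive statistics only.

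Three places bear on what happens after a repair:
- Section 2.1 counts as end of study "discontinuation from study before that for any reason, for example due to AAA repair".
- Section 5.1.2 says that for a patient who leaves because the aorta needs an operation, "the preoperative CT will be used for analysis in the study". Section 4.2 says only that such a scan may be used.
- Section 4.2 lists aortic surgery as a reason to stop study treatment, and asks patients whose treatment is stopped to stay in the study.

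**The concern.** The first two conditions concern adherence to the protocol. The third is different: for surgery and rupture, meeting it largely means having reached month 60 without the event. Someone repaired at month 30 has at most a CT from about that time. Remaining in the study does not help, because a CT after repair no longer measures growth of the untreated aneurysm. So the set in which surgery and rupture are to be compared is defined partly by their absence. At the interim, the 24-month version does the same to events before month 24.

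At stake is a planned table that could show few or no operations in either arm beside a real difference in the ITT analysis, and a per-protocol cost ratio whose denominator is close to zero. Per-protocol quality of life would largely describe patients who were not operated on, and so could not show a benefit from avoiding surgery.

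**Working it through.** The point is mainly one of logic, so the rules are set side by side first and the arithmetic is used only for scale.

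**Who can be an event in the per-protocol set?**

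| Patient | 60-month growth measure? | Event counted per protocol? |
|---|---|---|
| Repaired before month 60, pre-operative CT not accepted as the 60-month measure | No | No |
| Same patient, pre-operative CT accepted (growth is a rate in mm/year, 8.2.1) | Arguably yes | Yes |
| Rupture with no follow-up CT that qualifies | No | No |
| Pre-operative CT inside the 4-week window either side of month 60 (Table 1) | Yes | Yes |
| First found at 55 mm or more on the 60-month CT, with need for surgery read as in 1.2.2 | Yes | Yes |

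No section chooses between the first two rows. On the strict reading, repairs performed and ruptures are about 0 in each arm. The denominator of the cost ratio is then 0 − 0 = 0.

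**Scale.** Inputs from 8.4 are mean growth of 3 mm/year, SD 2.17 and a 30% reduction, which gives 3 × 0.7 = 2.1 mm/year on metformin. These inputs reproduce the plan's own figure: a difference of 0.9 mm/year with SD 2.17, 80% power and two-sided 0.05 needs 92 per arm, or 184 in total.

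My assumptions are: men, linear growth at a normally distributed rate, and reaching 55 mm as a stand-in for need for surgery. The event is baseline + 5 × growth ≥ 55. The documents do not give the baseline distribution, so it is varied.

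| Scenario | Control | Metformin | Difference |
|---|---|---|---|
| Baseline uniform on 30–49 mm | 48% | 34% | 14 points |
| Baseline skewed to small sizes | 37% | 24% | about 13–14 points |
| Uniform, half the growth, same coefficient of variation | 16% | 9–10% | about 6 points |
| Skewed, half the growth | 5% | 2% | about 2–3 points |

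**How much could remain in the set?** Suppose crossings up to month 48 are found and repaired, while later ones are first seen on the 60-month CT. With uniform baselines, 11.5% of controls and 9.3% of metformin patients cross after month 48. That is 0.115/0.483 = 24% and 0.093/0.341 = 27% of all crossings. With skewed baselines the shares are 36% and 41%.

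Leaving aside compliance and other drop-out, the uniform case gives:
- Removed before month 60: 48.3 − 11.5 = 36.8% of controls and 34.1 − 9.3 = 24.8% of metformin patients.
- Events among those left: 11.5/(100 − 36.8) = 18.2% and 9.3/(100 − 24.8) = 12.4%.
- Difference: 5.8 points, against 48.3 − 34.1 = 14.2 points overall.

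The ratio of the two risks barely moves in this example (0.68 against 0.71). What shrinks is the absolute difference, which is what cost per procedure avoided depends on. The month-60 window alone rescues little: about 1.5–1.7% of patients cross 55 mm within a month either side of it.

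**The case against.** A reader might infer that the per-protocol event count is zero by construction, that the cost ratio is certainly undefined, and that the whole simulated difference would vanish. The documents do not support this.

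Section 5.1.2 commits to using the pre-operative CT, growth is a rate that an earlier scan can supply, and nothing says that such a scan fails the condition. Section 1.2.2 glosses need for surgery as a diameter of at least 55 mm, which the 60-month CT can itself reveal. The simulated event is being at 55 mm or more at month 60, so part of it stays in the set, as shown above.

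The rates are also soft. The 48% for controls exceeds the 30% total drop-out planned in 8.4 and sits poorly with the expectation of few events in 8.3. The baseline distribution is assumed, and the SD is treated as a constant true rate for each patient over five years.

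Nor would a real harm be hidden. ITT is the main analysis and reports the events, no per-protocol test of events is specified, and the interim harm rule in section 10 is not tied to the per-protocol set.

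All of this stands against the stronger reading. It does not remove the core problem. The condition is worded as a measure at 60 months, no section says that an earlier pre-operative scan qualifies, and a rupture without a qualifying CT stays excluded. Counting only patients first found at 55 mm on the final CT is still a selected comparison, and the cost ratio is framed in procedures.

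**Conclusion.** The concern holds in a limited form. As worded, 8.1 uses a 60-month CT measure to choose the patients in whom surgery, rupture, quality of life and cost are compared, and that choice depends on the event. The per-protocol event comparison is near zero for repairs performed and ruptures on the strict reading, and depleted and selected on the more generous readings. The per-protocol cost per procedure avoided is accordingly undefined or unstable.

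The fall from about 14 to about 6 points is illustrative only. It rests on assumed baseline diameters, linear growth and detection of earlier crossings by month 48. The consequence is confined to a supportive analysis. It deserves correcting because the correction is nearly free, but the main results do not depend on it.

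**What to change.** In 8.1:
- Limit the third per-protocol condition to the growth outcomes (CT diameter, CT volume, ultrasound diameter), and state whether a pre-operative CT satisfies it.
- For surgery and rupture, quality of life and cost-effectiveness, either define membership by compliance and major deviations up to the event or end of follow-up, with no later CT required, or say that these outcomes are analysed in the ITT set only.

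Sections 2.1, 4.2 and 5.1.2 must also be reconciled on whether a patient stays in follow-up after AAA repair and on how the pre-operative CT is used.

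This takes a few sentences and no new data. The small downside of the first option is that the per-protocol number differs between outcomes and has to be shown for each.
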